Robinson ¹⁴ (1 mg/kg q24h; n = 19)	0.40	-	-	-	-

Study Justification

Ideal enoxaparin dose for VTE prevention in high-risk trauma patients is unknown. Predictors and explanations for low anti-Xa are also unknown. With emerging evidence demonstrating around 50% of trough anti-Xa concentrations are subtherapeutic and associated with increased VTE risk, the purpose of this study is to compare AT-III serum concentrations as a predictor of low anti-Xa. Secondly, the study will compare two enoxaparin dosing. Ultimately, this information can be used to develop an optimum protocol for patient-specific enoxaparin dosing for VTE prevention to improve patient outcomes.

METHODS**Study design**

This is an investigator-initiated, single-center, prospective, non-blinded, randomized controlled trial. Multi-system trauma patients between 18-80 years old admitted to the University of Cincinnati Medical Center (UCMC), an urban American College of Surgeons-verified Level 1 trauma center will be identified by the Trauma Surgery team. The trauma team will inform study personnel of these patients once enoxaparin is initiated. These patients will be screened for inclusion in the study. Patients who meet inclusion criteria will be administered informed consent by study personnel in their rooms. Patients in the surgical intensive care unit (SICU) and on the surgical floor are eligible for enrollment if all other inclusion and exclusion criteria are met. Informed consent will be obtained prior to enrollment. Goal enrollment is 200 patients with 100 patients in the control group and 50 patients in each randomization group.

Research data collection/study procedures

Patients will be screened daily by the trauma team. Research personnel will be alerted to potential patients for enrollment.

Intervention

Serum AT-III and anti-Xa will be drawn eight hours after the third dose of enoxaparin 30 mg q12h. Serum assays after at least the third dose should approximate drug steady state trough concentrations. Patients with a serum anti-Xa ≥ 0.1 IU/mL will remain on enoxaparin 30 mg every 12 hours and will be the control group. Patients with undetectable anti-Xa (intervention groups), defined as a trough anti-Xa < 0.1 IU/mL, will be randomized to receive either:

- a. Enoxaparin 40 mg every 12 hours (group 1)
- b. Enoxaparin 30 mg every eight hours (group 2)

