Coordinated serum anti-Xa, AT-III, and TEG will be collected as previously described. Time to goal anti-Xa achievement will be collected as previously described. Additional data to be collected include patient sex, age, weight, body mass index (BMI), body surface area (BSA), injury mechanism (blunt vs. penetrating), ISS, abbreviated injury score ([AIS] for head, chest, abdomen, extremity, cervical spine, thoracic spine, and lumbar spine), RAP, admission and highest serum creatinine, admission and lowest creatinine clearance (Cockcroft and Gault calculated), admission unit (e.g., ICU; floor), time to enoxaparin initiation, heparin initiation (days and number of doses) prior to enoxaparin therapy, VTE events specified, length of stay (hospital and ICU), 28-day mortality, major and minor bleeding events, overall mortality, interruption of study drug, cumulative fluid balance from admission with each serum assay, total milliliters of transfused fluid to date at each anti-Xa assessment, and milliliters of packed red cells transfused in specified time frame.

Specimen collection

Serum assays will be collected as previous described. In summary, initial AT-III and anti-Xa concentrations will be performed eight hours after the third dose of enoxaparin 30 mg q12h. Repeat anti-Xa assessment will be performed after the third dose of the new enoxaparin regimen, based on patient randomization. Coordinated AT-III and TEG will be performed with the first anti-Xa assessment and the first repeat assessment in the interventional group. After the initial assessments, weekly anti-Xa and AT-III will be collected on patients requiring dose adjustment for up to 28 days. All serum anti-Xa and coordinated AT-III and TEG will be drawn 30 minutes prior to stated dose.

Subjects will have the serum assays drawn by either nursing staff via central catheter access or phlebotomy via peripheral venous access. All labs will be drawn using two 2.7 mL blue top, sodium citrate tubes. One tube is needed for the TEG, while the other is used for the AT-III and anti-Xa.

Potential Benefits

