VTE are associated with a high morbidity and mortality. Optimal LMWH dosing has not been established for critically injured patients who have altered pharmacokinetics due to altered volume of distribution and metabolism, variable age and weight, and potential decreases in AT-III. Subtherapeutic serum anti-Xa trough concentration has been associated with increased risk for VTE. This pilot clinical investigation has the potential to revolutionize enoxaparin dosing and VTE prevention through anti-Xa guided dosing. Thorough evaluation of risk factors for reduced anti-Xa may provide a focused assessment of patients requiring anti-Xa assessment and subsequent dose adjustments. Overall, optimal enoxaparin dosing will result in fewer VTE events without increasing bleeding risk with an anti-Xa driven adjustment. Improved patient outcomes, expansion of scientific knowledge, and development of VTE prevention protocols may result.

Potential Risks, Discomforts, and Inconveniences

Level of Risk

VTE risks with inadequate prophylaxis have been previously justified above. Risks of increased enoxaparin doses include major and minor bleeding events. Risks will be mitigated by appropriate exclusion of patients with low body weight and increased serum creatinine / decreased creatinine clearance. Serum assays for risk of bioaccumulation will be performed weekly with subsequent dose reduction. Additionally, patient serum creatinine and creatinine clearance will be assessed daily by the trauma team with appropriate therapy modification should patient's renal function worsen. Patients with a 50% change in serum creatinine or an absolute change in serum creatinine by 1 mg/dL will be removed from the study. If these changes in renal function occur after patient has received initial laboratory assessment (i.e., anti-Xa; AT-III; TEG) will be included in the primary outcome analysis.

Blood volume loss due to serum anti-Xa, TEG, and AT-III assay as described above is minimal (2.7 mL x 2). Patients requiring peripheral vein access for serum assays will be at risk for pain/discomfort, bruising, fainting, and infection from phlebotomy sites.

Data Safety Monitoring Plan

Collected data will be screened for adverse events. [name] will act as medical monitor and review collected data and all adverse events to ensure patient safety.

Data Analysis

Primary Endpoints

1. Initial AT-III activity between the control group and the intervention group.

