2. Proportion of patients reaching goal anti-Xa between group 1 and group 2 overall, at first repeat assessment, and at second repeat assessment.
3. Median time to achievement of goal anti-Xa between group 1 and group 2.

Secondary Endpoints

1. Patient outcomes to be compared between control and intervention groups including all VTE events (i.e., pulmonary embolism; upper extremity deep venous thromboembolism [DVT]; proximal lower extremity DVT; distal lower extremity DVT), major bleeding (i.e., hemoglobin decrease of ≥ 2 g/dL in a 24 hour period requiring ≥ 2 units of packed red blood cells while on enoxaparin; worsened or new intracranial hemorrhage while on enoxaparin; repeat surgical intervention due to hemorrhage while on enoxaparin), minor bleeding (minor gastrointestinal bleeding [coffee ground emesis with or without < 2 units packed red cell transfusion needed while on enoxaparin]; interruption of study drug by trauma team; other overt bleeding not characterized a major while on enoxaparin), total transfusion requirements after 48 hours until discharge or admission day 28.
2. Proportion of patients with enoxaparin bioaccumulation (defined as an anti-Xa ≥ 0.3 IU/mL at any assay) between group 1 and 2.
3. Risk factor determination for low anti-Xa.

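### The hemoglobin criterion for major bleeding requires no identified bleed and makes no provision for planned surgery, so qualifying operative blood loss on enoxaparin counts as a major bleed

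*Combined protocol and SAP*

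**What the plan says.** Data Analysis, Secondary Endpoints, item 1 defines major bleeding as a closed list of three criteria separated by semicolons:

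- The first is a laboratory and transfusion rule: "hemoglobin decrease of ≥ 2 g/dL in a 24 hour period requiring ≥ 2 units of packed red blood cells while on enoxaparin".
- The second concerns bleeding inside the skull that is new or has progressed during treatment.
- The third, the only one that mentions an operation, reads "repeat surgical intervention due to hemorrhage while on enoxaparin".

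The same item then defines the minor category, which closes with a residual entry, "other overt bleeding not characterized a major while on enoxaparin". That is the only place in the bleeding definitions where overtness is a condition.

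The outcome is used as follows: "Patient outcomes to be compared between control and intervention groups including all VTE events", with major bleeding, minor bleeding and transfusion listed after VTE.

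Three other places bear on the point. Study design describes the population: "Multi-system trauma patients between 18-80 years old admitted to the University of Cincinnati Medical Center". Data Collection lists "major and minor bleeding events, overall mortality, interruption of study drug" among its items but names no operation date, operation type or operative blood loss. The Data Safety Monitoring Plan has one person "act as medical monitor and review collected data and all adverse events to ensure patient safety", with no rule for classifying endpoint events.

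**The concern.** The first criterion combines a laboratory value, a transfusion volume and a timing condition. It cannot tell apart two quite different patients. One has a planned fracture fixation, loses blood as expected, drops from 10.2 to 8.0 g/dL (a fall of 2.2) and receives 2 units. The other has a retroperitoneal bleed with the same fall and the same transfusion. If both count as on enoxaparin, both are major bleeds.

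The authors probably had clinical bleeding in mind. The minor category speaks of overt bleeding, and the surgical criterion is restricted to re-operation for hemorrhage. But that surgical criterion is a separate route to an event and does not restrict the first.

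The stake is how readable a safety outcome is in a pilot that sets out to evaluate safety. Events that reflect scheduled surgery raise the count in every group. Equal loads pull the risk ratio toward 1. The listed comparison is control against intervention, and those groups are formed by the first anti-Xa result, not by randomization, so equal loads cannot be taken for granted.

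**Working it through.** **Step 1: does any other text narrow the criterion?**

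| Place | What it covers | Does it narrow the first criterion? |
|---|---|---|
| Third major-bleeding criterion | Return to surgery because of hemorrhage | No; it is an alternative route |
| Minor-bleeding residual category | Overt bleeding that is not major | No; it applies only to minor bleeding |
| Inclusion Criteria, contraindications to chemical prophylaxis | Ongoing hemorrhage when prophylaxis is considered | No; it does not address operations after enoxaparin has started |
| Data Safety Monitoring Plan | Safety review by a medical monitor | No; no classification rule is given |

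The criterion does carry its own limits. The fall, the 2 units and the on-enoxaparin condition must all be met, so only the heavier operative losses qualify. How the last condition applies when doses are held around an operation is not stated.

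**Step 2: size, under assumption.** The plan gives no expected bleeding rate, operation rate or power for bleeding in this trial, so there is no figure to reproduce. Inputs:

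- True major bleeding *p*: 3% control, 9% intervention (assumed).
- Proportion *o* with a qualifying operative event: 0%, 2%, 5%, 10%, equal in both groups and independent of true bleeding (assumed).
- 100 patients per group (Study design: 100 control, and 50 + 50 randomized).

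Counted rate = 1 − (1 − *p*)(1 − *o*). For example, at *o* = 5%: control 1 − 0.97 × 0.95 = 7.85%; intervention 1 − 0.91 × 0.95 = 13.55%; ratio 13.55 / 7.85 = 1.73.

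| *o* | Control | Intervention | Risk ratio | Difference (points) | Exact Fisher power, two-sided 5% |
|---|---|---|---|---|---|
| 0% | 3.0% | 9.0% | 3.0 | 6.0 | 33% |
| 2% | 4.9% | 10.8% | 2.2 | 5.9 | 25% |
| 5% | 7.9% | 13.6% | 1.7 | 5.7 | 19% |
| 10% | 12.7% | 18.1% | 1.4 | 5.4 | 14% |

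The ratio is diluted markedly, while the absolute difference hardly moves. Power is low even in the first row. With a smaller assumed contrast, 1% versus 3%, the ratio falls from 3.0 to 1.7, 1.3 and 1.2, but power stays between 3% and 5% throughout, so there is none worth losing.

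**Step 3: unequal load.** Suppose true bleeding is 2% in both groups.

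- Operative events 5% control, 10% intervention: 1 − 0.98 × 0.95 = 6.9% and 1 − 0.98 × 0.90 = 11.8%, a ratio of 1.7 with no true difference.
- The same loads reversed: 11.8% and 6.9%, a ratio of 0.6.

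These loads are invented to show that either direction is possible. Nothing in the documents says which applies, or that either does.

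**The case against.** The strongest reply is that this is a matter of wording. The heading is bleeding, the intent is visible, and a sensible assessor would not score routine surgery as a bleed. The criterion is also narrow, since three conditions must coincide and doses may be held around an operation. Every rate above is assumed, and bleeding was never powered. An objective laboratory-and-transfusion rule is moreover an asset in a non-blinded trial: replacing it with a judgement about overt bleeding would let knowledge of the regimen influence classification.

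Much of this stands. The frequency is unknown, the power argument is weak, and the last point shapes the fix, which keeps the objective rule. What does not stand is reliance on unwritten judgement. The stated rule includes these events, and leaving each unblinded assessor to depart from it is less safe than a written timing rule.

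Three stronger readings are tempting and are not supported:

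- A reader might infer that operative events could never be separated afterwards. Data Collection introduces its list as items included, the attached database is not visible here, and the subject log links study number to medical record number, so chart review may recover operation dates.
- A reader might infer a particular direction of bias, because the Background associates edema with low trough anti-Xa. Nothing in the documents links edema or anti-Xa to operative burden.
- A reader might treat major bleeding as the principal safety outcome. The plan lists it as one component of a secondary endpoint.

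**Conclusion.** The point holds as a gap in a secondary endpoint definition and is worth correcting. As written, any planned-operation loss that meets both thresholds while the patient counts as on enoxaparin is a major bleed, and no other part of the plan changes that.

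Its size cannot be derived from the documents. The dilution in the ratio rests on assumed rates and on an operative load that is equal between groups and independent of true bleeding. An unequal load could push control versus intervention either way. Between the two randomized groups the load should be roughly balanced, so dilution is the main effect there. It should not be inferred that operative events are unrelated to the regimen: greater blood loss at surgery on a higher dose would itself be a safety signal.

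**What to change.** 1. Keep the first criterion, and the major-bleeding total built on it, as defined.
2. Add operation date and time to the Data Collection list, obtained by chart review.
3. Flag, by a fixed timing rule written in advance, each first-criterion event within 24 hours of a planned operation without return to theatre for hemorrhage. For each event, also note whether an overt or imaging-confirmed bleed was documented.
4. Report major bleeding by group both with and without the flagged events, and state that a flag does not mean unrelated to the regimen.
5. State how the on-enoxaparin condition is applied for this classification when doses are held around an operation. This concerns outcome counting only and implies nothing about when doses should be held.

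The cost is one extra chart-review field, a few lines of definition and a second tabulation. No event disappears from the report, and the timing flag needs no judgement about whether bleeding was abnormal.

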Droege ¹⁷	14.5%	5.5%	390
2013 UCMC Trauma Registry VTE	5.5%	2.5%	1468
2013 UCMC Trauma Registry VTE	5.5%	4.5%	6576

Data storage and confidentiality (include sample storage if applicable)

A single, central, electronic database will be constructed using Microsoft Excel® for storing all study-related data (attached). The database will be password protected such that only authorized study personnel can access the data. Data will be maintained in a confidential manner with regular reminders of the need for confidentiality provided from the senior investigator. A single subject log will be kept for matching patient study number, initials, medical record number, and admission date (attached). Once assigned to the log, patients will only be evaluated using their de-identified, study number. Data entered into the electronic database will be de-identified.

Once the study has been completed, the electronic database will be maintained in a locked office, per the IRB specifications. Only study personnel will have access to the data. Once the IRB-approved time has elapsed, all materials will be destroyed.

Study Population

Patients admitted to the UCMC trauma service are eligible for enrollment.

Inclusion Criteria

- a. Patients with an anticipated length of stay of at least 72 hours
- b. High-risk patients initiated on enoxaparin 30 mg every 12 hours per the existing VTE prophylaxis protocol
 - a. High-risk is defined as patients with a risk assessment profile (RAP) ≥ 5 .¹⁹
 - b. Trauma team VTE prophylaxis protocol contraindications to chemical prophylaxis include
 - i. Intracranial bleeding (e.g., chemical prophylaxis contraindicated within 24 hours of documented stable head computed tomography [CT]),
 - ii. Incomplete spinal cord injury with hematoma within 24 hours post-injury
 - iii. Ongoing hemorrhage
 - iv. Uncorrected coagulopathy
 - v. \geq grade IV liver or spleen injury
 - vi. Intraocular injuries.
- c. Age 18 – 80 years old

Exclusion Criteria

- a. Renal dysfunction (creatinine clearance < 30 mL/min or patients on continuous renal replacement therapy)
- b. Weight < 50 kg or > 150 kg
- c. Platelet count $< 50 \times 10^3$
- d. Allergy to heparin or low molecular weight heparins
- e. Patients on therapeutic anticoagulation at admission or requiring it within 24 hours of admission
- f. Isolated intracranial hemorrhage
- g. Known hyperbilirubinemia (defined as serum bilirubin > 6.6 mg/dL; interferes with the anti-Xa chromogenic assay)

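### The closed list that defines major bleeding files some of the most serious bleeds as minor, or in neither class, when they miss the haemoglobin and transfusion criterion

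*Combined protocol and SAP*

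**What the plan says.** Under Data Analysis, Secondary Endpoints, item 1, major bleeding is introduced by i.e., so the list reads as complete. It has three criteria:

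- (a) "hemoglobin decrease of ≥ 2 g/dL in a 24 hour period requiring ≥ 2 units of packed red blood cells while on enoxaparin"
- (b) "worsened or new intracranial hemorrhage while on enoxaparin"
- (c) "repeat surgical intervention due to hemorrhage while on enoxaparin"

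Minor bleeding covers minor gastrointestinal bleeding, "interruption of study drug by trauma team", and a catch-all: "other overt bleeding not characterized a major while on enoxaparin".

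The outcome items listed under Data Collection include "28-day mortality, major and minor bleeding events, overall mortality, interruption of study drug". Cause of death is not listed. The Data Safety Monitoring Plan has a medical monitor review adverse events, but it gives no rule for adjudicating or reclassifying a bleed.

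Inclusion criterion b lists the trauma team's contraindications to chemical prophylaxis. They include "Incomplete spinal cord injury with hematoma within 24 hours post-injury", intraocular injuries, and, from that grade upward, "grade IV liver or spleen injury".

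**The concern.** An endpoint with a closed major list and a catch-all minor class sorts each overt bleed by whether it matches the list, not by how serious it is. Here the list has no criterion for death from bleeding. It names one critical site, and it recognises a procedure only if that procedure is surgical and a repeat. The population makes the gaps realistic. Liver and spleen injuries below grade IV are eligible, and the spinal haematoma contraindication lapses 24 hours after injury.

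Safety is part of the pilot's stated purpose, and bleeding is the named risk of the higher doses. Potential Benefits expects fewer VTE events with no increase in bleeding. The background reports no major bleeding in earlier studies, so readers will look first at whether this trial's major count is zero. A serious bleed filed beside coffee-ground emesis would distort that reading.

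**Working it through.** **Step 1. Apply the criteria to each type of bleed.** This is a reading of the text; no arithmetic applies.

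| Event on enoxaparin | (a) | (b) | (c) | Class |
|---|---|---|---|---|
| Intracranial bleed, fatal or not | not needed | yes | not needed | Major |
| Bleed with re-operation, fatal or not | not needed | no | yes | Major |
| Fatal extracranial bleed, no re-operation, (a) missed | no | no | no | Minor if overt |
| Spinal bleed costing function but little blood | no | no | no | Minor if overt; if concealed, possibly neither |
| First laparotomy for a bleeding spleen or liver, (a) missed | no | no | no, it is not a repeat | Minor if overt |
| Embolisation, (a) missed | no | no | only if read as surgery, and as a repeat | Minor if overt |
| Expected loss at a scheduled operation, fall of 2 g/dL and 2 units required | yes | no | no | Major |

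Rows 3 to 6 are under-classified. The last row errs the other way, because (a) asks for neither overt nor unplanned bleeding.

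**Step 2. Look for a repair elsewhere.** Mortality is collected without cause of death, so the listed data cannot show that a death was a fatal bleed. Pooling major with minor does not help: minor includes drug interruption by the trauma team, with no bleed required by the wording.

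**Step 3. Size of one event.** The plan gives no bleeding rate, sample size or power for bleeding, so there is no figure of its own to reproduce. Inputs are the planned group sizes from Study design: 100 control, 50 + 50 randomised.

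- Control against intervention, as item 1 states: 1/100 = 1 percentage point per event.
- Per randomised arm, the view that specific aim 2 could support: 1/50 = 2 percentage points per event.

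The exact two-sided 95% upper limit for x events in n is the p that solves P(X ≤ x | n, p) = 0.025. For x = 0 it is 1 − 0.025^(1/n).

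| Events | n = 100 | n = 50 |
|---|---|---|
| 0 | 3.6% | 7.1% |
| 1 | 5.4% | 10.6% |
| 2 | 7.0% | 13.7% |

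**Step 4. Effect on the planned test.** The plan uses Fisher's exact or chi-square at p < 0.05. By Fisher, 0 against 2 gives p of about 0.50 with either 50 or 100 per group. With 0 in one group, at least 6 are needed in the other for p < 0.05, again at either size.

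**Step 5. Illustration under assumed rates.** None of these inputs is in the documents. Assume that 2% to 8% of patients have a serious bleed and that half of these miss all three criteria. The chance that an arm of 50 records no major bleed is (1 − q)^50, where q is the rate that is counted.

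- True 2%: 0.98^50 = 36% if all are counted; 0.99^50 = 61% if half are missed.
- True 4%: 0.96^50 = 13%; 0.98^50 = 36%.
- True 8%: 0.92^50 = 1.5%; 0.96^50 = 13%.

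**The case against.** The strongest reply is that serious events are not lost. Overt bleeds are still counted as minor, transfusion is an endpoint to discharge or day 28, deaths are counted, and the medical monitor sees all adverse events. Bleeding is an unpowered secondary endpoint in a pilot, and the statement about bleeding risk is an expectation under Potential Benefits, not a hypothesis with a margin. Intraocular injury is a contraindication with no time limit, so bleeds there should be rarer. All of this stands and limits the importance of the point, but it does not correct the label on the event.

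A reader might infer more than the text supports, in four ways:

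- That every fatal bleed is minor unless transfusion is heavy. Intracranial and re-operated bleeds are already major. Criterion (a) also speaks of units required, not units given, so some patients who die before transfusion could still meet it.
- That criterion (a) demands the transfusion within the same 24 hours, so that prompt transfusion hides the fall. The 24 hours attach to the haemoglobin fall; transfusion timing is not stated. Any masking calculation would also need a haemoglobin rise per unit, which the documents do not give.
- That major bleeding is under-counted overall. Scheduled operative loss can add to the count, so the net sign is unknown.
- That one or two misfiled events would reverse the planned comparison. Step 4 shows that they would not.

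**Conclusion.** The point holds in a limited form. On the plain wording, fatal extracranial bleeds without re-operation, overt bleeds at critical sites other than intracranial, and bleeds needing a first operation or embolisation are under-classified whenever they miss criterion (a). Concealed ones may not be classified at all. Only the size per event can be stated: 1 percentage point for the stated comparison, 2 points within a randomised arm. What is at stake is the descriptive safety statement, above all whether the report says none or some.

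This rests on three readings: that i.e. closes the list, that repeat surgery does not include a first operation, and that no separate adjudication rule exists. It also assumes that enrolment reaches the planned group sizes. The change is worth making because the rule itself gives the wrong class and correcting it is cheap.

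**What to change.** In Secondary Endpoints, item 1:

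1. Replace criterion (c) with *any unplanned surgical or interventional-radiology procedure for hemorrhage*.
2. Add *fatal bleeding*.
3. Add *new or worsened symptomatic bleeding at a non-intracranial critical site (e.g. spinal, intraocular)*. Requiring symptoms keeps incidental imaging changes out of the major class.
4. In criterion (a), exclude falls explained by blood loss at a scheduled operation.

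In Data Collection, add cause of death.

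The cost is endpoint wording and a few more chart fields; dosing, visits and sample size do not change. The reported major-bleeding rate may be slightly higher. The current definition can be reported alongside, so that readers see the effect of the change.
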